Cognitive Behavioral Therapy (CBT-I) is the first line of treatment for insomnia (Rybarczyk, Lund, Mack, & Stepanski, 2009; Schutte-Rodin, Broch, Buysse, Dorsey, & Sateia, 2008; Siebern & Manber, 2011). It has moderate to large effects among Veterans, with improvements documented up to 6 months (between-group effect sizes=0.5-0.8; 10-11% more time asleep in bed at post-treatment and 6mo) (Edinger et al., 2009; Germain et al., 2014; Karlin, Trockel, Taylor, Gimeno, & Manber, 2013; Taylor et al., 2018). Research with college students (Fucito et al., 2017; Hershner & O'Brien, 2016) and animal models (Vengeliene, Noori, & Spanagel, 2015) suggests that improvements in insomnia may reduce heavy alcohol use, and pharmacological treatment of insomnia has been found to delay relapse among individuals with alcohol use disorder (AUD) (Anton et al., 2011; Brower et al., 2008). Based on this research, **CBT-I is expected to reduce insomnia symptoms among heavy-drinking Veterans**, thereby resolving insomnia-related deficits in executive functioning, negative emotionality, and craving for alcohol, as well as use of alcohol as a sleep aid. **These improvements, in turn, are expected to reduce alcohol use and related problems.** This line of research is particularly promising for Veterans, as Veterans generally perceive stigma toward mental health treatment (Vogt et al., 2014) but indicate interest in treatment for insomnia (Hom et al., 2016; Plach & Sells, 2013; Shepardson, Funderburk, Pigeon, & Maisto, 2014).

4. Study Procedures

This research will examine the efficacy of CBT-I in improving sleep and alcohol use outcomes among heavy-drinking OEF/OIF/OND-era Veterans. Forty-four Veterans will be randomized to receive sleep hygiene or to participate in five sessions of individual Cognitive Behavioral Therapy for Insomnia (CBT-I). Outcomes will be assessed at baseline, mid-treatment (3 weeks), post-treatment, and 3-month follow-up (see Figure 1).

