Penn Alcohol Craving Scale. The Penn Alcohol Craving Scale is a 5-item measure of alcohol craving in the past week. Participants rate the intensity, frequency, and duration of cravings, as well as their ability to resist acting on those cravings and their overall “average alcohol craving” for the past week. This measure has demonstrated good internal consistency and construct validity (Flannery, Volpicelli, & Pettinati, 1999).

8. Study Statistics

Power analysis. We chose to utilize G-Power, rather than a power analysis specific to multilevel modeling (MLM, sometimes referred to as mixed modeling) because powering for ANOVA will ensure we are adequately powered for MLM analyses, which will increase power to detect significant effects. Based on previous studies, the expected effect size is large for insomnia outcomes (based on trials with Veterans) (Germain et al., 2014; Talbot et al., 2014), medium for alcohol use outcomes (based on trials with college students) (Fucito et al., 2017), and medium for executive functioning outcomes (based on trials with fibromyalgia patients) (Miro et al., 2011). We used G-Power to determine the sample size needed for an a priori repeated measures ANOVA, within-between interaction ($\alpha = .05$, power = .95, groups = 2, repetitions = 4, correlation = .40). Based on these calculations, the sample size required to detect a small effect ($f = .10$) is 260; a medium effect ($f = .25$) is 44; and a large effect ($f = .40$) is 18. Assuming 2/month recruitment and 35% attrition, we plan to recruit 68

participants over 34 months to obtain a final sample of 44 participants. This will provide us with an adequate sample size to detect moderate to large group by time interactions.

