Data analysis. All questionnaire and behavioral task data will be scored according to published conventions. We will test for group equivalence in gender, age, race/ethnicity, use of sleep medication (# LRD), use of other drugs, and perceptions of peer drinking quantities (descriptive norms) at baseline. Group differences are unexpected in the context of randomization; however, if one of these variables is associated with both group and a given outcome variable, we will include it as a covariate in the prediction of that outcome. Data will be screened for integrity, outliers, missing values, and violations of the assumptions of MLM. Outliers will be replaced with the value that is 3 standard deviations +1 unit above the mean (Tabachnick & Fidell, 2007), and missing values will be handled in MLM using full maximum likelihood estimation.

Cohen's *d* and 95% CIs will be used to examine the magnitude of between-group differences mid-treatment, post-treatment, and at 1-month follow-up. We chose MLM over other statistical approaches because it requires fewer assumptions and has superior ability to handle missing data. In each model, the Level 1 variable will be time. Level 2 portions of the model will include the effect of condition and necessary covariates. The impact of CBT-I on insomnia symptoms will be tested by regressing condition on the Level 1 intercept and time effect. We will examine whether attrition is associated with any baseline variables and control for such variables when necessary. We will also explore CBT-I effects on alcohol use and proposed mediators, though we will be underpowered to detect small to moderate effects. We will use MLM to examine the within-individual associations between insomnia symptoms and alcohol use.

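### The plan uses 44 both as the number randomised and as the number left after 35% attrition, and its two power statements overlap at a medium effect

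*Combined protocol and SAP*

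**What the plan says.** **Number of participants.** Section 1 (Abstract) assigns 22 participants to CBT-I and 22 to sleep hygiene. The opening of Section 4 (Study Procedures) also gives 44 as the number randomised. Section 4, Recruitment, cites attrition of 19–38% in CBT-I trials with Veterans, takes 35%, and recruits 68 over 34 months for a final sample of 44. Section 8, Power analysis, repeats the 68, the 35% and the 44, then concludes: "This will provide us with an adequate sample size to detect moderate to large group by time interactions".

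**Power.** Section 8, Power analysis, uses a repeated measures ANOVA group-by-time interaction (alpha .05, power .95, 2 groups, 4 repetitions, correlation .40). It finds totals of 260, 44 and 18 for f = .10, .25 and .40, which it labels small, medium and large. It says "the expected effect size is large for insomnia outcomes (based on trials with Veterans"), "medium for alcohol use outcomes (based on trials with college students") and "medium for executive functioning outcomes (based on trials with fibromyalgia patients").

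**The second power statement.** Section 8, Data analysis, says the effects of CBT-I on alcohol use and the proposed mediators will be explored, "though we will be underpowered to detect small to moderate effects". Section 3 names executive functioning as one of the proposed pathways.

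**The concern.** One number cannot be both the count randomised and the count remaining after attrition unless all the attrition comes first. The distinction matters because 44 is the number that delivers the planned power at a medium effect. If it is the starting number, the analysis will normally hold less information than the power statement assumes. If it is the finishing number, Sections 1 and 4 understate how many are randomised. A reader cannot tell which is meant, or how many are expected to complete.

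The two power statements add to this. For alcohol use and executive functioning, the effect the plan expects (medium) lies in the range that one paragraph calls adequately powered and at the top of the range that the next calls underpowered. Alcohol measures are listed as primary outcomes in Section 7a, so a null alcohol result would be read against one of these two sentences.

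**Working it through.** **Step 1. Reproduce the plan's figures.** Inputs from Section 8, Power analysis: alpha = .05, k = 2 groups, m = 4 repetitions, r = .40. The test is a noncentral F with λ = f²·N·m/(1 − r), df1 = (k − 1)(m − 1) = 3 and df2 = (N − k)(m − 1).

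| f | N | λ | df2 | Power |
|---|---|---|---|---|
| .10 | 260 | .01·260·4/.6 = 17.33 | 774 | 95.1% |
| .25 | 44 | .0625·44·4/.6 = 18.33 | 126 | 95.7% |
| .40 | 18 | .16·18·4/.6 = 19.20 | 48 | 95.6% |

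All three sample sizes reproduce. So does the inflation: 44/(1 − .35) = 67.7, rounded up to 68; 68 × .65 = 44.2; 68/2 per month = 34 months.

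**Step 2. Compare the possible readings of 44.**

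- *68 recruited, 24 lost before randomisation, 44 randomised.* This fits every count. It uses up the whole 35% and leaves no stated allowance for loss after randomisation.
- *68 randomised, 35% lost afterwards, about 44 complete.* This fits the recruitment and power text but not the 22 + 22 in Section 1 or the 44 randomised in Section 4.
- *44 randomised, 35% lost afterwards.* 44 × .65 = 28.6, so about 29 complete. This fits Sections 1 and 4 and the source of the 35%, but not a final sample of 44.

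**Step 3. Power under the third reading, f = .25.**

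- N = 28: λ = .0625·28·4/.6 = 11.67, df2 = 78, power 80.8%.
- N = 29: λ = .0625·29·4/.6 = 12.08, df2 = 81, power 82.3%.

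These are complete-case figures. The plan uses full maximum likelihood, which keeps the partial records. Assume 35% lost completely at random (all after baseline, in equal stages, or all after post-treatment) and a group difference over the four visits of (0,0,d,d), (0,d,d,d), (0,d/2,d,d) or linear. Power at f = .25 with 44 randomised is then about 84–95%. The top of that range needs late dropout.

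**Step 4. The two power statements at N = 44.** λ = f²·44·4/.6 = 293.3·f².

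| f | λ | Power |
|---|---|---|
| .10 | 2.93 | 26% |
| .196 | 11.27 | 80% |
| .25 | 18.33 | 95.7% |

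Effects from f = .10 up to about f = .20 are underpowered by the usual 80% standard, and f = .25 is not. The statements can be reconciled if moderate in the Data analysis text means something below f = .25, but the text does not say so. The threshold also depends on Step 2: with 28–29 completers, complete-case power only just passes 80% at f = .25 itself.

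**Step 5. What f = .25 means as a between-group d.** For differences d_j at the four visits, in within-cell SD units and zero at baseline, f = SD(d_j)/2. So f = .25 corresponds to d = 1.00 for (0,0,d,d), 1.15 for (0,d,d,d), 1.21 for (0,d/2,d,d), 1.34 for a linear pattern and 1.41 for (0,d/2,d,d/2). The plan states no time pattern, so the range is about 1.0–1.4.

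**The case against.** **Loss before randomisation.** Sections 1 and 4 both say 44 are randomised, and no section says 68 are. Consent is given at baseline. Randomisation follows a two-week at-home eligibility phase, and the payment schedule requires seven consecutive diaries for eligibility. So 68 consented and 44 randomised is a coherent design. This stands as a possible reading, and a reader should not infer that the plan intends to randomise 68. It does not settle the matter. The 35% is drawn from attrition in CBT-I trials rather than from a screening-failure rate, and on this reading later loss is assumed to be nil. The missing-data text in Section 8 fits either reading. So does the definition of recruitment in Section 7a, which concerns only the CBT-I arm.

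**Complementary ranges.** Adequate for moderate to large and underpowered for small to moderate can be read as two ranges that meet. Step 4 largely supports that, and the second group of analyses is labelled exploratory. What remains is the overlap at exactly the effect the plan expects.

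**A stronger reading to resist.** Section 3 says of CBT-I: "It has moderate to large effects among Veterans, with improvements documented up to 6 months (between-group effect sizes=0.5-0.8". Setting that beside d of 1.0–1.4, a reader might infer that the adequacy sentence is false. The documents do not support this. Section 3 does not name its metric and is not the power input. Section 8 defines its terms on the f scale, where the sentence is true for 44 analysed, and it expects a large effect for insomnia. Any d-scale power figure also depends on an assumed time pattern and on the test. The planned test is not the omnibus ANOVA: "The impact of CBT-I on insomnia symptoms will be tested by regressing condition on the Level 1 intercept and time effect".

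**Pilot purpose.** Feasibility is the first objective, alcohol efficacy is called preliminary, and Cohen's d and "95% CIs will be used to examine the magnitude of between-group differences mid-treatment" and at later visits. This limits the harm from a misread null result but does not tell the reader how many are randomised.

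**Conclusion.** The concern holds as an inconsistency in the stated sample size, with a smaller overlap between the two power statements. There is no arithmetic error in 260, 44, 18 or 68.

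Size: if 44 are randomised and 35% are then lost, complete-case power at f = .25 is about 81–82% against the planned 95%. Maximum likelihood narrows the gap and, with late dropout, nearly closes it. If all 24 are lost before randomisation and nobody afterwards, the 95.7% stands. If 68 are randomised and about 44 complete, it stands on a complete-case basis.

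These figures rest on the plan's own ANOVA settings. The maximum likelihood range also assumes loss completely at random and the four time patterns listed. The power overlap is confined to effects near f = .25. It is a matter of an undefined word, not of two incompatible calculations.

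This should be fixed, because the number randomised and the power claim are basic figures and correcting them is cheap.

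**What to change.** 1. State one number randomised in Sections 1, 4 and 8, and say when the 35% loss is assumed to occur. If 68 are randomised, correct Section 1 and the opening of Section 4. If 44 are randomised, give the loss expected after randomisation and restate power at f = .25 for the number expected to complete (about 81–82% complete-case if 35% are lost, with a note that maximum likelihood recovers part of this).

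2. Make the two paragraphs of Section 8 agree by giving the f value below which the alcohol and mediator analyses are underpowered: for example, below about f = .20 for 80% power with 44 analysed. Use the same meaning of moderate in both.

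3. Optionally, note beside the adequacy sentence that f = .25 in this 2 × 4 interaction (r = .40, arms equal at baseline) corresponds to a between-group d of about 1.0–1.4 depending on the time pattern, so moderate there does not mean d = 0.5. Any power figure quoted on the d scale should be for the multilevel model test actually planned.

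Cost: a wording amendment, with no added enrolment or data. The sponsor must commit to one number randomised, and the stated power may become less favourable.

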As of April/May of 2022, BuildClinical will manage all digital marketing recruitment for this study. BuildClinical is a data-driven digital marketing company that helps academic researchers recruit participants for research studies more efficiently using social media, software, and machine learning. They will ensure that all IRB-approved guidelines and procedures are followed during recruitment. They use study-specific advertisements to engage participants on digital platforms such as Facebook, Google, WebMD, etc. Participants who click on the advertisements will be redirected to a study-specific landing page. On the landing page, the person can complete an online pre-screen questionnaire. Pre-screening data is then routed to BuildClinical's Secure Socket Layer (SSL) software, which encrypts all information to keep it private and HIPAA compliant. Their backend servers are stored in secure data centers in the USA.

Interested individuals will have the option of (a) completing the screening survey online, either via Qualtrics or BuildClinical, or (b) calling project staff to learn more about the study. In CBT-I trials with Veterans, attrition rates have ranged from 19 to 38% (Edinger et al., 2009; Germain et al., 2014; Karlin, Trockel, Spira, Taylor, & Manber, 2015). Estimating an attrition rate of 35%, we will recruit 68 participants over 34 months to obtain a final sample of **44 participants**. Approximately 9% of Veterans are women and 12-15% have PTSD; therefore, randomization will be stratified by gender and PTSD.

Screening. Individuals who are interested in the study will complete a brief eligibility screen online from remote locations and provide their first name, phone number, and email.

A research assistant will contact those who provide this information to explain the study in more detail and, if they are still interested, schedule them for the baseline assessment. Interested individuals whose only barrier to participation is travel/in-person appointments will be scheduled for a remote baseline visit.

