At-home assessment. Participants who report symptoms of sleep apnea and attend baseline in person will be asked to wear the holter monitor/electrocardiogram (SpaceLabs Healthcare EVO device) for one night in their own homes and in their own bed to rule out diagnosis of sleep apnea. The research assistant will prepare eligible participants who screen positive for sleep apnea for this assessment using SpaceLabs Healthcare EVO devices. Monitoring will be completed in accordance with recommendations for sleep assessment (Stein & Pu, 2012). HRV monitoring will provide an index of autonomic arousal (which has been linked to sleep impairment) and an apnea hypopnea index (a measure of sleep apnea). Participants who demonstrate an apnea hypopnea index greater than 15 will be referred for polysomnography and treatment of sleep apnea.

All participants will also be asked to wear the actiwatch 24/7 and complete two full weeks of daily sleep diaries to confirm diagnosis of insomnia (>30min sleep onset latency or wake after sleep onset 3+ nights per week). Sleep diaries will be collected electronically and time-stamped each morning using the Qualtrics data management system. Participants will be asked to complete the diary each morning before noon. Those who have not completed the diary by noon will receive a reminder text or phone call from study staff.

Randomization. Participants who are eligible based on the at-home assessment will be randomized to the CBT-I or sleep hygiene only conditions.

Table 1. Assessment, therapy, and payment schedule

Week	Assmt	CBT-I	Paymt	Bonus
1	BL		30	
2		S1	20	20
3		S2		
4	Mid-tx	S3	20	
5		S4		
6	Post-tx	S5	20	
7		(S6)	30	30
8				
9				
10				
11				
12				
13				
14				
15				
16				
17				
18				
19				
20	3mo		50	
21			40	40

Note. 1mo = 1-month. Assmt = assessment. BL = baseline. Bonus = bonus payment (for completion of all previous 14 days of sleep diaries). Paymt = standard payment. Tx = treatment.

Return baseline assessment visit. Participants will be informed of their condition following the two weeks of at-home assessment. During their return visit, one of the research assistants will also provide all participants with a one-page handout on sleep hygiene, which will include personalized normative feedback on their alcohol use. The research assistant will walk the participant through the sleep hygiene handout and answer any questions they may have about the information.

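### Covariates are picked outcome by outcome from baseline tests, the stratification factors are not committed to the model, and baseline means are left free by arm; prespecified adjustment would be cheap and would narrow the per-visit intervals by about 7% at the plan's own correlation

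*Combined protocol and SAP*

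**What the plan says.** All modelling text is in the combined protocol and SAP, section 8 (Study Statistics), Data analysis.

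- **Covariates.** The plan opens with "We will test for group equivalence in gender, age, race/ethnicity, use of sleep medication", continues the list with other drug use and perceived peer drinking, and then applies the rule "if one of these variables is associated with both group and a given outcome variable, we will include it as a covariate". A second route follows: "We will examine whether attrition is associated with any baseline variables and control for such variables when necessary".
- **Model.** "Level 2 portions of the model will include the effect of condition and necessary covariates". For the treatment test, "The impact of CBT-I on insomnia symptoms will be tested by regressing condition on the Level 1 intercept and time effect". The plan does not say whether time is linear or categorical, or whether slopes are random.
- **Per-visit estimates.** Cohen's d and "95% CIs will be used to examine the magnitude of between-group differences mid-treatment, post-treatment" and at a follow-up visit. No baseline adjustment is named. (This sentence calls the last visit 1-month, whereas the schedule has a 3-month visit; that is a separate inconsistency and does not alter the arithmetic here.)
- **Design.** Section 4, Recruitment: "Approximately 9% of Veterans are women and 12-15% have PTSD; therefore, randomization will be stratified by gender and PTSD". Section 4, Randomization: "Participants who are eligible based on the at-home assessment will be randomized to the CBT-I or sleep hygiene only conditions". The baseline survey and the two-week at-home assessment therefore come before allocation.

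**The concern.** Three features sit badly together.

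1. The covariate rule depends on observed group imbalance and observed association, with no stated test or cut-off, and runs separately for each outcome. Section 7a lists many primary outcomes, so each could be analysed with a different model that nobody could have written down in advance.
2. Gender and PTSD were important enough to stratify on, but gender is only a candidate on the screening list and PTSD is not on that list at all. PTSD could enter only as an undefined necessary covariate or through the attrition clause.
3. Because allocation follows baseline, the arms have equal expected baseline means. Letting condition act on the intercept spends information on estimating a difference that randomisation sets to zero in expectation.

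At stake is the width of the per-visit intervals, which will carry much of the efficacy message in a pilot with about 22 per arm, and the ability to show that the models were fixed in advance. The feasibility and acceptability objective is not affected.

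**Working it through.** **Inputs.** From section 8, Power analysis: alpha .05, power .95, 2 groups, 4 repetitions, correlation .40, f = .25 for N = 44, 35% attrition. From the abstract: 22 per arm. Section 8 gives no SDs, so results are in SD units.

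**The plan's own figure.** For the within-between interaction, λ = f²·N·m/(1−ρ) = .0625 × 44 × 4/.60 = 18.33, with 3 and 126 degrees of freedom. Power is .957, so N = 44 reproduces. The other two sample sizes also reproduce (260 for f = .10, 18 for f = .40), and 44/.65 = 67.7, rounded up to 68. Sample size is not the issue.

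**Per-visit difference, 22 per arm.**

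- Unadjusted half-width: t(.975, 42) × √(2/22) = 2.018 × .3015 = .608 SD.
- Baseline-adjusted: t(.975, 41) × √[(2/22)(1−r²)(1+1/40)], where the last factor is the cost of estimating the baseline slope. At r = .40: 2.020 × √(.0909 × .84 × 1.025) = 2.020 × .2798 = .565 SD.
- Reduction: 1 − .565/.608 = 7.1%. In 40,000 simulated trials the mean reduction was also 7.1%. The gain is worth about 7 participants, since (.608/.565)² × 44 ≈ 51.

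| r | adjusted half-width (SD) | narrower by |
|---|---|---|
| .2 | .604 | 0.7% |
| .3 | .588 | 3.3% |
| .4 | .565 | 7.1% |
| .5 | .534 | 12.3% |

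**Does the planned mixed model already capture this?** Under compound symmetry with ρ = .40, complete data and categorical time, the SE of a visit difference is √(2/22) = .3015 with free baseline means, the same as unadjusted. With a common baseline mean it is √(.84 × 2/22) = .2763. So with categorical time the planned parameterisation gains nothing at a single visit.

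**Entry cut.** Entry requires an Insomnia Severity Index of at least 10 on a 0–28 scale, which may restrict the baseline spread. If .40 is the unrestricted correlation and the baseline SD shrinks by a factor u (both assumptions), the correlation becomes ru/√(1−r²+r²u²). At u = .75 this is .31 and the gain is 3.7%; at u = .6 it is .25 and the gain is 2.0%.

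**Stratifiers.** Adding gender and PTSD, balanced and unrelated to outcome (39 df), moves .565 to .566 SD, a cost of about .001. If they behave as unbalanced non-prognostic covariates, the factor becomes 1+3/38 and the half-width .581 SD: a cost of about .016, leaving a net gain of 4.6%.

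**Condition-by-time effect (secondary).** With four visits, ρ = .40, equal SDs, complete data and no random slope, a common baseline mean removes 19% of the variance (linear in Table 1 weeks 1, 4, 6, 20), 33% (linear in visits 0–3) or 30% (categorical: 1 − .84/1.20). With baseline SD 0.75 of follow-up these fall to 9%, 16% and 13%. With a random slope whose variance over follow-up equals the outcome variance, the two linear figures are 10% and 17%, or 4% and 7% if the baseline SD is also 0.75.

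**A trap.** Linear time with a common baseline mean forces the arm difference to be a straight line through zero. At Table 1 weeks, the mid-treatment difference becomes (4−1)/(20−1) = 3/19 of the 3-month difference, with a half-width of about .085 SD. That precision comes from the straight-line assumption, not from the data.

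**The case against.** The strongest reply is that the 7% rests on reading a silence. Section 8 does not say whether d and its intervals are raw or model-based, and the same paragraph names multilevel modelling as the analysis. If they come from the planned model with linear time and free baseline means, the half-widths at Table 1 weeks 4, 6 and 20 are about .47, .45 and .60 SD, two of them already below .565. This stands, and it makes the 7% conditional. It does not remove the point: those narrower widths depend on a straight-line difference from week 1 to week 20, while treatment ends around weeks 6–7, and the plan does not commit to that form.

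A second reply is that .40 is a planning correlation between repeated measures, not an observed baseline-to-follow-up value. This also stands; at r = .2 the gain is negligible and the stratifiers could cancel it.

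A third is that, with 35% attrition planned, dropping covariates that predict both dropout and outcome could bias a likelihood analysis. That is right, and the attrition provision should stay in the main model.

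A reader might infer that the planned test is invalid, that the trial is too small, or that the plan ignores baseline. The documents support none of these. The test is valid, N = 44 reproduces, and if the baseline assessment is a response row the condition-by-time term uses it as change from baseline. A reader might also take the 19–33% variance reductions as the expected gain; they hold only under equal SDs and no random slope, neither of which the documents establish.

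**Conclusion.** The point holds as a cheap improvement, not as a flaw that invalidates the analysis. On the text, all three features are present: data-driven covariates by outcome, stratifiers not committed to the model, and baseline means free by arm. The prespecification gain does not depend on any correlation.

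The precision gain is about 7% of half-width (.608 to .565 SD) for the per-visit intervals. It assumes 22 per arm, r = .40, and intervals that are unadjusted or taken from a categorical-time model with free baseline means. It ranges from 0.7% at r = .2 to 12% at r = .5 and shrinks if the entry cut lowers the correlation. It is an average: in about 11% of simulated trials the adjusted interval was the wider one. No precision gain is claimed from the stratifiers; they align the analysis with the randomisation and replace selection by imbalance.

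**What to change.** Replace the test-then-adjust rule with wording such as:

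> For each outcome measured at baseline, between-group effects at each visit are estimated from a mixed model with categorical visit and condition-by-visit terms, arm means constrained equal at baseline (baseline kept as a response), and gender and PTSD as fixed main effects. This model supplies the per-visit adjusted differences and 95% CIs; Cohen's d divides the adjusted difference by the unadjusted pooled SD at that visit. Baseline characteristics are reported descriptively and are not used to select covariates by group imbalance. The existing provision to control for baseline variables associated with attrition is kept.

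Do not take per-visit differences from a linear-time model with a common baseline mean, for the 3/19 reason above. Use main effects only for the stratifiers: if the 44 mirrored the section 4 percentages (assumption), there would be about 4 women (44 × .09) and 5–7 participants with PTSD (44 × .12 to .15), with fewer than one expected in the crossed cell if independent (44 × .09 × .15 = .6).

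**Cost.** A few sentences and no new data, since both factors are already needed for randomisation. The stratifiers use two degrees of freedom: about .001 SD of half-width if balanced, up to about .016 SD if not. Keeping the attrition provision leaves one data-dependent route to covariates, which is the price of protecting the missing-data handling.
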